#### **8.3 SAE Report Form**

SAEs (including AEs of special interest, as applicable) related or at least possibly related to escitalopram/placebo will be recorded on the FDA Form 3500A (MedWatch for Industry Form FDA 3500A –Mandatory Reporting) but should only be reported as instructed below. This form can be found at the following link: <https://www.fda.gov/safety/medical-product-safety-information/medwatch-forms-fda-safety-reporting>

The electronic FDA SAE reporting forms should not be used.

The PI will evaluate all SAEs for relationship to study participation and report to IRB of record per applicable reporting policies.

#### **8.4 Reporting Procedures for Serious Adverse Events**

For the purposes of safety reporting, all adverse events determined to be related or possibly related to escitalopram/placebo will be reported that occur from the initiation of escitalopram/placebo on Day 1 until the Week 25 study visit. Adverse events both serious and non-serious, and deaths that occur during this period will be recorded in the source documents and reported according to AE reporting policies of the IRB of record. All SAEs should be monitored until they are resolved or are clearly determined to be due to a subject's stable or chronic condition or intercurrent illness(es). Related AEs will be followed until resolution to baseline or grade 1 or stabilization.

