#### Unblinding Procedures:

- Patients will be unblinded if study drug is discontinued for the Adverse Events of Special Interest (hemorrhage, suicidal ideation and mania) as described in Table 7.1.
- Patients will be unblinded if study drug is discontinued due to Grade 4 hyponatremia as described in Table 7.1.

- Patients will be unblinded if they meet the criteria for removal from study as defined in Section 6.2.
- Patients will be unblinded at the time of their Day 85 (Week 13) end of treatment visit.

Patients will be unblinded by IDS staff as outlined in the Unblinding Manual. Patients who are unblinded before they complete all study visits will be asked to continue to have study-related phone calls with study staff and complete all study-related questionnaires. Patients who are unblinded prior to the end of treatment visit and undergo tumor resection will be required to have the research tissue sample and post-surgery research blood samples taken.

An assessment of depression will be made by the treating physician. Based on the assessment, patients who received escitalopram may be given the option of continuing the medication either under the supervision of their medical oncologist or primary care provider. If this occurs, the patient will obtain escitalopram from commercial supply at the dose prescribed by the patient's medical oncologist, primary care physician or other provider.

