### **8.2.3 Adverse Event Evaluation**

The investigator or designee is responsible for ensuring that all adverse events, (both serious and non-serious as defined in previous sections) observed by the study staff or reported by the subject that are determined to be related or possibly related to escitalopram/placebo which occur after the initiation of escitalopram/placebo are fully recorded in the subject's medical record and reported according to AE reporting policies of the IRB of record. Adverse events attributed to chemotherapy and/or underlying disease will not be recorded for this study. Source documentation must be available to support all adverse events.

The investigator or sub-investigator (treating physician if applicable) will provide the following for all adverse events (both serious and non-serious):

- Event term (as per CTCAE)
- Description of the event
- Date of onset and resolution
- **Expectedness of the toxicity**
- **Grade of toxicity**
- **Attribution of relatedness to the investigational agent- (this must be assigned by an investigator, sub-investigator, or treating physician)**
- Action taken as a result of the event, including but not limited to; no changes, dose interrupted, reduced, discontinued, etc. or action taken with regard to the event, i.e. no action, received conmed or other intervention, etc.
- Outcome of event

Descriptions and **grading scales** found in the NCI Common Terminology Criteria for Adverse Events (CTCAE) version **5.0** will be utilized for AE reporting.

**An expected adverse event** is an event previously known or anticipated to result from participation in the research study or any underlying disease, disorder, or condition of the subject. The event is usually listed in the Investigator Brochure, consent form or research protocol.

**An unexpected adverse event** is an adverse event not previously known or anticipated to result from the research study or any underlying disease, disorder, or condition of the subject.

**Attribution** is the relationship between an adverse event or serious adverse event and the study drug. Attribution will be assigned as follows:

- Definite – The AE is clearly related to the study drug.
- Probable – The AE is likely related to the study drug.
- Possible – The AE may be related to the study drug.

- Unlikely – The AE is doubtfully related to the study drug.
- Unrelated – The AE is clearly NOT related to the study drug.

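### Safety events are recorded only if judged related to study drug, yet from Day 85 (earlier for some) that judgement can be made knowing the arm, so the same event can be kept on escitalopram and dropped on placebo

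*Combined protocol and SAP*

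**What the plan says.** **What is recorded.** Section 8.2.3 makes the investigator responsible for seeing that events "that are determined to be related or possibly related to escitalopram/placebo which occur after the initiation of escitalopram/placebo are fully recorded". It adds: "Adverse events attributed to chemotherapy and/or underlying disease will not be recorded for this study". Section 8.2.1 repeats that exclusion, and Sections 8.3 and 8.5 apply the relatedness condition to the SAE form and to OnCore entry.

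**Over what period.** Under Section 8.4, events judged related or possibly related "will be reported that occur from the initiation of escitalopram/placebo on Day 1 until the Week 25 study visit". The next sentence of 8.4 carries no such condition: "Adverse events both serious and non-serious, and deaths that occur during this period will be recorded in the source documents".

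**When the blind ends.** Section 6.1, Unblinding Procedures: "Patients will be unblinded at the time of their Day 85 (Week 13) end of treatment visit". Earlier unblinding is also provided for: "Patients will be unblinded if study drug is discontinued for the Adverse Events of Special Interest", namely hemorrhage, suicidal ideation and mania. The same applies to a stop for Grade 4 hyponatremia and to any Section 6.2 removal criterion.

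**Who attributes.** Section 8.2.3 says of relatedness that "this must be assigned by an investigator, sub-investigator, or treating physician". It names no blinded assessor, and its list of event fields includes no date of attribution.

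**The exception.** Section 8.2.4 requires Grade 2 or higher bleeding, mania and suicidal ideation to be recorded and reported, with no relatedness condition.

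**The concern.** In most trials attribution is a label on an event that is recorded anyway. Here it is the entry gate. While the assessor is blind, the gate works alike in both arms. Once the arm is known it need not. Nausea, diarrhea and fatigue are on the Section 8.1 list of escitalopram effects and are also plausible symptoms of cancer treatment, so attribution is a real judgement. In a patient known to have had placebo, such an event is easily put down to chemotherapy and goes unrecorded. In a patient known to have had escitalopram, who under Section 6.1 may by then be taking commercial drug at a prescriber's dose, it can be called possibly related and kept.

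At stake is the by-arm description of tolerability. Section 14.4 promises careful measurement of side effects, and Section 1.4 looks ahead to a phase III trial, for which an event table by arm would be read.

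**Working it through.** The plan gives no figure for event counts or attribution, so there is nothing of its own to reproduce. The power calculation in 14.3 does not enter.

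**1. Which events are exposed.** Setting 8.2.3, 8.2.4, 8.3 and 6.1 side by side:

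- Grade 2 or higher bleeding, mania, suicidal ideation: recorded in either arm under 8.2.4. What stays open to knowledge of the arm is the relatedness label and, through 8.3, whether the SAE form is completed.
- Grade 4 hyponatremia: triggers unblinding under 6.1 but is not on the 8.2.4 list. Exposed.
- Events behind other Section 6.2 removals, such as a safety decision by the investigator: exposed.
- Events found at the Day 85 visit: toxicity assessment (6.3) and unblinding (6.1) fall at the same visit, with no order stated. Exposed if the arm is revealed first.
- Other events from Day 85 to Week 25: exposed.

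**2. Share of calendar time.** Blinded dosing covers Days 1-84, which is 84 days. Week 25 runs from Day 24 × 7 + 1 = 169 to Day 25 × 7 = 175. The unblinded part is 169 − 85 = 84 to 175 − 85 = 90 days, about half of the window.

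**3. Share of assessments.** The Study Calendar has nine toxicity assessments: Days 1, 8, 22, 36, 50, 64, 78 and 85, and Week 25. One of nine falls after Day 85.

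**4. Recorded ratio when true rates are equal.** Let f be the share of events attributed after unblinding, a the share called related while blinded (the same in both arms), and aE and aP the shares called related after unblinding on escitalopram and placebo.

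Ratio = [(1 − f)a + f·aE] / [(1 − f)a + f·aP]

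All-or-none case, aE = a and aP = 0: ratio = 1/(1 − f).

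- f = 1/9 (events track assessments): 1/(8/9) = 1.125
- f = 2/9 (Day 85 events also attributed after the arm is revealed): 1/(7/9) = 1.29
- f = 0.25: 1/0.75 = 1.33
- f = 0.5 (events track calendar time): 1/0.5 = 2.0

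Study dosing ends at Day 84, so attribution may also fall on escitalopram. With aE = a/2 and aP = 0, the ratio is (1 − f/2)/(1 − f): 1.06 at f = 1/9 and 1.5 at f = 0.5. With aE = aP it is 1 at every f. All values of f, aE and aP are assumptions.

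**5. In patients.** Assume 23 per arm, the same 20% to 60% risk of an event after Day 85 in both arms, and half of escitalopram events called at least possibly related.

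- Escitalopram: 23 × 0.2 × 0.5 = 2.3 to 23 × 0.6 × 0.5 = 6.9 recorded patients.
- Placebo, attribution still 50%: the same 2.3 to 6.9.
- Placebo, attribution 10%: 23 × 0.2 × 0.1 = 0.5 to 23 × 0.6 × 0.1 = 1.4.
- Placebo, attribution 0%: none.

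**The case against.** The strongest reply has four parts.

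- **Three of the four named stopping events cannot be dropped.** A reader might infer that any event that stops treatment can vanish from the placebo arm. Section 8.2.4 does not support that for bleeding, mania or suicidal ideation. This stands and narrows the point.
- **The order may already be safe.** Table 7.1 is framed around drug-related toxicity, Section 7.0 ties other stops to a PI judgement of relatedness, and unblinding follows the stop. Details are left to an Unblinding Manual that is not among the documents and may add protection. This stands in part: it suggests an order for stopping events, but the protocol requires no signed and dated attribution, and none of it covers Day 85 to Week 25.
- **No safety comparison is planned.** Section 14.4 rules out statistical safety review, and 8.2.1 says side effects are not an endpoint. This stands: the effect is on descriptive data. A reader might infer that the QIDS result is compromised. The text gives no basis for that, since adverse-event attribution plays no part in the QIDS score.
- **The larger ratios are worst cases.** A reader might infer that escitalopram counts will be higher, even doubled. That needs half of all events to come after dosing ends, full retention on escitalopram and none on placebo. The documents show only that a difference can arise.

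The second sentence of 8.4 could also be read as recording everything. Section 8.2.3 says otherwise for events attributed to chemotherapy or disease, so the two passages need reconciling.

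**Conclusion.** The point holds for events attributed after the arm is known, mainly those outside the 8.2.4 list: Grade 4 hyponatremia, events behind other removals, events found at the Day 85 visit, and events up to Week 25. For bleeding, mania and suicidal ideation, only the relatedness label and the SAE form are exposed.

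The size cannot be determined from the documents. Under all-or-none attribution the recorded ratio is about 1.1 if events follow the assessment schedule and up to 2.0 if half fall after Day 85. It is smaller if escitalopram events are also called unrelated once dosing has ended, and 1 if attribution does not change with knowledge of the arm. The conclusion also assumes that the Unblinding Manual does not already lock attribution.

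This is a low-priority reporting matter, worth correcting because the correction is cheap.

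**What to change.** - **8.2.3:** require attribution to be assigned, signed and dated before IDS reveals the arm, both for early unblinding and for every event known at the Day 85 visit.
- **8.4 and 14.4:** list events by arm from Day 1 to unblinding as the blinded data. List events from unblinding to Week 25 separately, labelled unblinded, with commercial escitalopram use shown.
- **8.2.1, 8.2.3 and 8.4:** state that attribution does not decide whether an event reported at the Week 25 toxicity assessment is recorded. Without this, locking attribution at Day 85 would still let later placebo events drop out; splitting the listing would only show the gap. The same rule can cover calls held after an early unblinding.
- **8.4 against 8.2.3:** reconcile the second sentence of 8.4 with the exclusion in 8.2.3.

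The cost is one date field, one split in the listing, and a few more Week 25 events recorded. The field belongs in the study's own event record, since the SAE form is a fixed FDA form. No blinded follow-up is lost, because blinding already ends at Day 85. No dose, visit or stopping rule changes.

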##### **8.4.1 SAE Reporting Requirements**

- Participating investigators (all sites) must report all serious adverse events related to escitalopram/placebo to the Principal Investigator (e.g. Sponsor-Investigator) within **24 hours** of discovery or notification of the event. The participating investigator must also provide follow-up information on the SAE until final resolution.
  - [name], [contact]

- The Lead Site Principal Investigator will review the SAE and report the event to external collaborator(s), and IRB as applicable.
- It is the Sponsor-Investigator's responsibility (e.g. lead site PI) to ensure that ALL serious adverse events related to escitalopram/placebo that occur on the study (e.g. ALL SAEs that occur at each enrolling institution) are reported to all participating sites.

## **8.5 SAEs and OnCore**

- All SAEs related or possibly related to escitalopram/placebo will be entered into OnCore.
- A copy of the SAE form(s) submitted to the sponsor-investigator is also uploaded into Oncore.

## **8.6 Data Safety and Toxicity Committee**

It is the responsibility of each site PI to ensure that all SAEs related to escitalopram occurring on this trial (internal or external) are reported to the Case Comprehensive Cancer Center's Data and Safety Toxicity Committee. This submission is simultaneous with their submission to the sponsor and/or other regulatory bodies.

The sponsor-investigator is responsible for submitting an annual report to the DSTC as per CCCC Data and Safety Monitoring Plan.

## **8.7 Data and Safety Monitoring Plan (DSMP)**

This protocol will adhere to the policies of the Case Comprehensive Cancer Center Data and Safety Monitoring Plan in accordance with NCI guidelines.

## **9.0 PHARMACEUTICAL INFORMATION**

A list of the adverse events and potential risks associated with the investigational or commercial agents administered in this study can be found in Section 8.

### **9.1 Investigational Agents**

**9.1.1 Name of Agent** Escitalopram

Other Names: Lexapro

**Product description:** Escitalopram and placebo will be supplied as 10 mg capsules

**Formulation, Packaging and Labeling:** All aspects of drug and placebo manufacturing, preparation, packaging, and labeling will be managed by Buderer Drug Co. Escitalopram will be supplied as a 10mg oblong white tablet, commercially manufactured pharmaceutical by Aurobindo, supplied by Buderer Drug, over-encapsulation in a #1 dark blue capsule. Twenty (20) capsules placed into a labeled child resistant prescription vial. Eight (8) bottles will be supplied for each patient. Placebo is a white capsule containing microcrystalline cellulose, compounded (to match the weight of the escitalopram 10mg tablet) over-encapsulation into a #1 dark blue capsule. Twenty capsules placed into a labeled child resistant prescription vial. Eight (8) bottles will be

supplied for each patient. A batch will be prepared every 180 days or sooner as required. Bottles will be labeled with the patient's study number, blinded ID (B or D) and drug storage information.

**Storage requirements and stability:** Stability will be for six months duration, and stable at room temperature 15°-30°C (59°-86°F).

**Route of administration:** There will be no mixing or added preparation by pharmacists, technicians or nurses once the finished clinical supply is received from Budrer. Patients will take escitalopram or placebo at the standard dose, with a ramp up and ramp down interval as follows:

2 weeks: 10 mg (1 capsule)

8 weeks: 20 mg (2 capsules)

2 weeks: 10 mg (1 capsule)

**Drug Procurement:** Escitalopram and placebo for this study will be obtained from Buderer Drug Co.

**Drug Accountability:** Orders will be placed by study staff and product shipped by Buderer and stored at University Hospital's Investigational Drug Services Pharmacy at room temperature for the duration of the trial. Patients will be given one bottle of escitalopram/placebo upon study initiation for the first two weeks on study. At Day 15 patients will be given six bottles for the next eight weeks and at Day 71 patients will be given one bottle for the remainder of the study.

Investigational Drug Services Pharmacy is responsible for maintaining accurate dispensing records of the study drug.

**Drug Destruction:**

At the completion of the study, there will be a final reconciliation of drug shipped, drug consumed, and drug remaining. This reconciliation will be logged on the drug reconciliation form, signed and dated. Any discrepancies noted will be investigated, resolved, and documented prior to destruction of unused study drug. All unused investigational product/placebo will be destroyed at the site per institutional policy. Drug destroyed on site will be documented in the study files.

## **10.0 EXPLORATORY or CORRELATIVE STUDIES**

### **10.1 Serum Metabolites**

#### **10.1.1 Background**

Tryptophan is the principal substrate for serotonin synthesis, and therefore, tryptophan breakdown may have biologic implications on clinical depression in patients with dysregulated tryptophan catabolism. We and others have demonstrated that the enzymes responsible for tryptophan metabolism are dysregulated in pancreatic cancer . Specifically, the enzymes that divert tryptophan into kynurenone and related metabolites are overexpressed, including IDO1, IDO2, and TDO. This pathway effectively shunts tryptophan away from serotonin synthesis.

### **10.1.2 Rationale**

We will determine if a correlation exists between expression levels of these enzymes in the tumor and 1) depression at baseline, and 2) the development of depression in patients on trial. Additionally, serum levels (or plasma levels are a suitable alternative) of specific tryptophan metabolites will be measured in patients at the start of treatment. Patients undergoing resection will have repeat levels taken 1-2 months after resection to determine how tumor burden impacts metabolite levels.

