### **1.3 Correlative Studies**

The serotonin theory of depression is supported through clinical experience. Selective serotonin reuptake inhibitors (SSRIs) remain the most common class of medicines used to treat depression. Mechanistically, these drugs increase serotonin levels at brain synapses. Tryptophan is the principal substrate for serotonin synthesis, and therefore, tryptophan breakdown may have biologic implications on clinical depression in patients with dysregulated tryptophan catabolism. We and others have demonstrated that the enzymes responsible for tryptophan metabolism are dysregulated in pancreatic cancer. Specifically, the enzymes that divert tryptophan into kynurenine and related metabolites are overexpressed, including IDO1, IDO2, and TDO (. This pathway effectively shunts tryptophan away from serotonin synthesis.

In this study, we will examine the expression of each of these tryptophan degrading enzymes in resected PDAs (25 of 46 patients in the trial are expected to have resected specimens for analysis). We will determine if a correlation exists between expression levels of these enzymes in the tumor and 1) depression at baseline, and 2) the development of depression in patients on trial. Additionally, plasma levels of specific tryptophan metabolites will be measured in patients at the start of treatment. Patients undergoing resection will have repeat levels taken 1-2 months after resection to determine how tumor burden impacts metabolite levels.

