### **3.1 Study Characteristics**

Patients may be non-depressed or depressed. Those who are severely depressed according to the Quick Inventory of Depression Survey (QIDS  $\geq 16$  points) will be referred to a psychiatrist for further evaluation and possibly additional therapy, based on clinical judgement. The study will be started at University Hospitals Cleveland Medical Center with the possibility that it can be opened at alternative sites if needed for patient accrual.

At the time of study enrollment, the treating physician must have the intent to treat the patient with 12 weeks of neoadjuvant chemotherapy as standard of care cancer treatment. For this study, patients will be randomized in a 1:1 ratio to receive escitalopram or placebo using a randomization table prepared by the study statistician. This randomization table will be shared by the statistician only with the Investigational Drug Services Pharmacy (IDS) personnel and will detail for all 55 patients/study IDs whether that patient is to receive escitalopram or placebo. Each patient will be

assigned a study number, in sequential order, only after all eligibility criteria have been confirmed by the study coordinator, treating physician (Investigator or Co-investigator) involved in the case, and by a member of the Clinical Trials Unit's Quality Assurance department.

It is possible that burden of disease could influence mood. Therefore, patients will also be stratified according to whether they have resectable disease or locally advanced disease (borderline resectable or unresectable) according to NCCN criteria. A pancreatic surgeon (PI or Co-Investigator) will determine this status using the Tumor Profile Assessment (see Appendix VIII). The Tumor Profile Assessment is to be filled out by the PI or by the Co-investigator prior to randomization.

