### **3.4 Expected Duration of Treatment and Subject Participation**

Patients will be treated with escitalopram or placebo for 12 weeks. An end of treatment visit and assessment will be conducted at Week 13 and another at Week 25. After Week 25, patients will be followed every three months for three years for treatment details and to document disease and survival status.

The typical course of neoadjuvant therapy for resectable or unresectable patients is virtually always  $\geq 12$  weeks. Patients whose cancer progresses during that time will remain on study unless the patient meets criteria for removal from study as noted in Table 7.1 or if the patient becomes unable to swallow oral medications.

The first day of medication will be considered day = zero with respect to the depression (QIDS-SR, PHQ-9) and QOL (FACT-Hep) survey time points (Survival analyses however will be dated back to the date of consent). Surveys will be performed biweekly for 12 weeks. The FACT-Hep will be administered at a slightly less frequent interval (once per month). In the follow-up phase, beginning after Week 25, subjects will be followed for up to 3 years, for recurrence, treatment details, and survival information. Follow-up information will be obtained every 3 months.

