#### **4.2 Exclusion Criteria**

The presence of any of the following will exclude a subject from study enrollment.

- \_\_\_ 4.2.1 Patients under the age of 18 or over age of 80

- 4.2.2 Metastatic pancreatic or other periamppullary cancer
- 4.2.3 Resection of pancreatic cancer within the past year prior to study enrollment or planned surgery within the next 12 weeks
- 4.2.4 Currently on an antidepressant, anti-anxiety, anti-bipolar or anti-psychotic medicine. Patients who have taken MAOI inhibitors within the past 6 months are excluded.
- 4.2.5 Patients with a diagnosis of bipolar disease
- 4.2.6 Patients with a history of seizure disorder
- 4.2.7 Patients with a recent medical history of myocardial infarction or unstable heart disease
- 4.2.8 Patients with a history of QTc prolongation or torsade de points, a baseline QTc interval of > 500ms, a history of drug-induced QTc prolongation or congenital long QT syndrome
- 4.2.9 Patients with Child-Pugh score of B or C
- 4.2.10 Patients with moderate to severe renal disease with a GFR < 45.
- 4.2.11 Patients who cannot ingest oral medication
- 4.2.12 Patients with any history of mania
- 4.2.13 Patients with known allergy to escitalopram
- 4.2.14 Patients who are pregnant or lactating
- 4.2.15 Patients who do not speak English

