## **6.0 Treatment Plan**

### **6.1 Treatment Regimen Overview**

This interventional trial involves the administration of a safe and well-tolerated oral antidepressant. Patients will take escitalopram or placebo, at the standard dose, with a ramp-up and ramp-down interval, as previously described in a similar trial in head and neck cancer .

The schedule is as follows:

2 weeks: 10 mg/day (1 capsule)

8 weeks: 20 mg/day (2 capsules)

2 weeks: 10 mg/day (1 capsule)

Patients will come to the clinic on Day 1 and will be given a pill diary and enough blinded escitalopram/placebo for the first 2 weeks of the study. The patient will be taught how/when to take the pills and how to complete the pill diary. The patients will be given pill bottles for Weeks 1-2. Patients will take their first dose of escitalopram/placebo and have blood drawn for serum metabolites at this visit (prior to dosing). The QIDS-SR depression survey, PHQ-9, FACT-Hep QOL and FIBSER Side Effect Questionnaires (see Appendices IV, V, VI and VII) will be completed. A member of the study staff will give the questionnaires to the patient to complete in a private area. The study staff member will remain with the patient during completion of the questionnaires to assist, if necessary, and to ensure that the patient is answering all questions on their own.

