### **10.1.3 Collection of Specimens**

Blood samples will be collected on Day 1. For patients who undergo resection, samples will also be collected between one and three months after surgery to account for half-life of metabolites and determine if tumor burden influences metabolite levels. Approximately 30 ml blood will be collected into three red top tubes from each patient via venipuncture or port.

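### The Day 1 to post-surgery change in tryptophan-pathway metabolites is to be read as a tumor-burden effect, although the randomized drug and chemotherapy fall between the two draws and antidepressant use may continue afterwards

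*Combined protocol and SAP*

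**What the plan says.** Blood for metabolites is drawn twice. The first draw is on Day 1, before the first dose (6.1; Study Calendar, footnote 2). The second is taken only in patients who are resected. Section 10.1.2, in words that 1.3 repeats, says: "Patients undergoing resection will have repeat levels taken 1-2 months after resection to determine how tumor burden impacts metabolite levels". Section 10.1.3 gives the same purpose with a longer window (last word of the sentence cut): "samples will also be collected between one and three months after surgery to account for half-life of metabolites and determine if tumor burden influences metabolite". The Study Calendar and the follow-up list in 11.1.2 also use one to three months. The calendar has no metabolite draw between these two.

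On what happens in between:

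- Section 3.1: "patients will be randomized in a 1:1 ratio to receive escitalopram or placebo". Section 3.4: "Patients will be treated with escitalopram or placebo for 12 weeks".
- Criterion 4.1.5 requires at least 12 weeks of planned neoadjuvant chemotherapy. Criterion 4.2.3 excludes patients with "planned surgery within the next 12 weeks".
- After unblinding at Day 85, 6.1 says that "patients who received escitalopram may be given the option of continuing the medication" from commercial supply. Sections 1.2 and 7.0 (Safety Assessment) allow additional therapy, including a second drug, for patients in either arm with severe scores.

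The assays are for kynurenine, melatonin and serotonin (10.1.6). On SSRIs, 1.3 states: "Mechanistically, these drugs increase serotonin levels at brain synapses". Section 14 contains no metabolite analysis.

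**The concern.** The stated reading of the before-after change names one cause, the tumor. At least two other exposures fall between the draws by design: the randomized drug in about half the patients, and chemotherapy in all of them. The drug was chosen because it acts on serotonin, and serotonin is one of the measured quantities. If the change is pooled over arms and read as 10.1.2 and 10.1.3 describe, any drug effect still present at the second draw goes into the tumor-burden result.

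Arm alone does not settle who is exposed at that time. Escitalopram patients may stop or continue after Day 85, and placebo patients may have been prescribed an antidepressant. No text explicitly requires antidepressant use to be recorded at the second draw. Medication review belongs to the history, which is scheduled at screening and Day 85 (Study Calendar, footnote 1).

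At stake is the interpretation of one correlative result. The primary QIDS analysis and the quality-of-life analysis are not affected.

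**Working it through.** The plan gives no sample size, test or effect size for the metabolite change, so there is no figure to reproduce.

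**Sequence for a patient treated as planned.** Day 1 draw before dosing; study drug on Days 1-84 alongside chemotherapy; unblinding at Day 85, with optional continuation of escitalopram; resection; second draw one to three (or one to two) months later. The whole randomized course lies between the draws.

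**Number of patients.** Sections 1.3 and 10.2.2 expect 25 of 46 patients to have resected specimens. That figure is for tissue and is used here as an approximation for paired bloods. At 1:1 this is about 12 on escitalopram and 13 on placebo. Ignoring stratification, there is about a 96% chance that between 8 and 17 of the 25 are on escitalopram.

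**Bias of a pooled change.** If the drug shifts the change by d in a fraction f of patients, the pooled mean is shifted by f × d. With 12 of 25 affected, f = 12/25 = 0.48. With 6 of 25, f = 6/25 = 0.24.

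**Illustration.** Simulation with 40,000 runs, 25 patients, true tumor effect zero, one-sample t-test, two-sided 5%. The drug effect d, in SDs of the within-patient change, is an assumption; the documents give none.

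| d (SD) | Bias, 12 affected | False finding, 12 affected | Bias, 6 affected | False finding, 6 affected |
|---|---|---|---|---|
| 0 | 0 | 5% | 0 | 5% |
| 0.5 | 0.48 × 0.5 = 0.24 | 20% | 0.24 × 0.5 = 0.12 | 8% |
| 1.0 | 0.48 | 54% | 0.24 | 16-17% |
| 1.5 | 0.72 | 83% | 0.36 | 27% |

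The column for 12 affected is an upper scenario. It needs every escitalopram patient to continue the drug, or its effect to persist in full to the second draw.

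**After the fix.** In the placebo arm alone (13 patients) the randomized drug contributes no bias, and the false-positive rate stays at about 5% for every d. The change detectable with 80% power at two-sided 5% rises from 0.58 SD (n = 25) to 0.85 SD (n = 13). These are t-test values; the normal approximation (1.96 + 0.84)/√n gives 0.56 and 0.78. The difference between arms in the change (13 versus 12) is detectable only at about 1.17 SD.

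**The case against.** The strongest reply is that this is a purpose clause, not an analysis. Tumor burden against metabolites is not among the objectives in section 2. Section 14 prescribes no pooled test, and arm is known for everyone by Day 85, so a split by arm is always available. That stands. A reader might infer that the plan commits the trial to reporting a drug effect as a tumor effect; the documents do not go that far. They state the interpretation and leave the separation unspecified.

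Four other stronger readings are tempting and should not be drawn:

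- *Half the patients are on an SSRI at the second draw.* Study drug ends on Day 84 and the draw comes at least a month after surgery. On the planned course, patients who stop are therefore at least about a month off drug. Continuation is only an option after an assessment, so the share could be well below half.
- *Antidepressant use at that draw is not captured.* Treatment details are collected at Day 85, Week 25 and every three months, in follow-up by record review, visit or phone, and might recover it. But 6.3 describes long-term follow-up as cancer-specific, so recovery is not assured.
- *Serum serotonin shifts by a known percentage.* Section 1.3 speaks only of brain synapses. The documents give no figure for blood and do not link SSRIs to kynurenine or melatonin.
- *Without an end-of-treatment sample, the efficacy-marker objective in 2.2 fails.* That objective asks about association with efficacy, which the Day 1 samples and the tissue can address.

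**Conclusion.** The concern holds as a limit on interpretation. As described, the Day 1 to post-surgery change mixes any effect of the tumor's removal with chemotherapy, surgery and any drug effect still present, and the stated attribution to tumor burden alone is not supported. The bias is the affected share times the drug effect. The share is at most about half if exposure comes only from the escitalopram arm and that arm makes up half of those resected, and is probably lower. The drug effect has unknown size and direction and could be zero at the second draw. The false-positive rates above are illustrations that rest on an assumed effect and on 25 paired samples.

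Separating by arm removes the randomized drug from the placebo contrast. It does not remove chemotherapy, or antidepressants prescribed to placebo patients, so the wording of the conclusion must change as well. Because the gap concerns a correlative aim and is cheap to close, it is worth correcting.

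**What to change.** In 10.1.2 and 10.1.3, and in 1.3 where the wording is repeated:

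1. Record on the post-surgery sample form any antidepressant taken since Day 85, with drug and dates.
2. Report the change by randomized arm, with the placebo arm as the main contrast and the between-arm difference shown. Use antidepressant use at the second draw only as a descriptive or sensitivity split. Making it the main selection would choose patients on a post-randomization factor probably related to depression, which these markers are meant to explain.
3. Describe the result as change across chemotherapy plus surgery, not as the effect of tumor burden alone.
4. Reconcile the one-to-two-month and one-to-three-month windows and use one throughout.

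This costs one form field and some analysis wording, with no added visit or sample. The real price is precision: about 13 rather than 25 patients in the main contrast. The between-arm difference can only be descriptive, since it detects about 1.17 SD at best and compares a subset defined by resection after randomization.
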